7.9.1.3 Determination of Subjects for Analysis

The primary objective will be analyzed using the FAS. All subjects with an attempted implant of the Micra TPS will be included in the analysis.

7.9.1.4 Missing Data for Primary Endpoint

Missing data may occur if a successfully implanted subject discontinues from the study without experiencing a major complication related to the Micra TPS and/or procedure prior to the 6-month visit. Data from such subjects is included in the primary analysis up until their censoring date, but it is unknown if these subjects would experience an event following their censoring date. Should the issue of missing data arise, the reasons for the missing data will be summarized to assess the plausibility that the missing data could change the statistical inference.

The Worst-Case Scenario Analysis will only be performed if it is identified as a true missing (e.g. permanent missing of AE-related data, and subsequently resulting in non-conclusive CEC review). The sensitivity analysis may count such missing data as failures.

A Tipping Point Analysis will only be performed if it is identified as a true missing (e.g. permanent missing of AE-related data, and subsequently resulting in non-conclusive CEC review).

In the event the CEC adjudicates an AE with an "Unknown" classification relationship to the Micra TPS and/or procedure, and the subject has no other failure events within 6 months post implant, a sensitivity analysis will be conducted to consider those subjects as failures at the time of the first "Unknown" classification event.

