14.1.6. Stopping Rule

No interim analysis is planned for this study. Therefore there is no stopping rule defined. The analysis will be conducted after data collection is completed, verified and locked.

14.1.7. Analysis Data Set, handling of missing data, non-compliance, error or non-reasonable data entry.

Statistical analysis procedures (procedures) will strictly comply to SOP of the Medical Research & Biometric Center, National Center for Cardiovascular Diseases. Please refer to other relevant documents for additional details.

Data entry error or non-reasonable values will be cleaned before data analysis. In the event of subject exit or withdrawal of consent, the subject will still be included in the final statistical analysis. The specific reasons for subject exit or withdrawal will be provided in detail in the statistical report. If no data can be collected from a subject during post-implant follow-up, additional sensitivity analysis may be performed.

This study will use the survival analysis method for the primary objective. Scenarios for censoring are previously defined. The Worst Case Scenario Analysis will only be performed if it is identified as a true missing (e.g. permanent missing of adverse event related data, and subsequently resulting in non-conclusive CEC review) or if the cause of death is unknown. The sensitivity analysis may count such missing data as failures.

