7.9.1.2 Statistical Analysis Method

All subjects who undergo an Micra implant procedure will be included in the analysis. The Kaplan-Meier survival analysis will be used to estimate the probability of a subject free from Micra TPS and/or procedure related relate major complications. The log-log transformation will be used to calculate the 95% confidence limits.

Definitions:

- Endpoint event for the survival analysis is Micra TPS and/or procedure related major complications, defined as those AEs resulting in:
 - Death
 - Permanent loss of device function due to mechanical or electrical dysfunction of the device (e.g. pacing function disabled, leaving device abandoned electrically)
 - System revision (reposition, replacement, explant)
 - Hospitalization
 - Prolonged Hospitalization by 48 hours or more

The CEC will determine if the AE is related to Micra TPS and/or procedure; and if the AE is a major complication. **Note:** Only system or procedure-related AEs will be classified as a major complication, minor complication or an observation. In the event the CEC provides an "Unknown" classification relationship to the Micra TPS and/or procedure, the event will not be considered "Related" for the primary endpoint analysis. Refer to section 7.9.1.4 for additional information.

- Censoring occurs in subjects who do not experience any Micra TPS and/or procedure related major complications
- Follow-up time: from the date of Micra implant procedure to
 - the onset date of a Micra TPS and/or procedure related major complication, or
 - study termination date (e.g. subject exit, die, or study closure, etc.), or
 - the date of Micra deactivation due to any reason that is not related to the Micra TPS or procedure (e.g. device system upgrade, the subject's other comorbidities, etc.), or
 - the last follow-up date, if none of the above occurs.

The statistical analysis of the primary objective will be 2-sided, using 0.05 significance level. The statistical analysis software package SAS will be used to conduct these analyses.

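### The SAP's Unknown-relatedness sensitivity analysis counts AEs of any severity as failures, so it does not test the primary endpoint

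*SAP*

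**What the plan says.** **Primary endpoint.** Protocol 6.2.1 and SAP 4.1 and 7.9.1.2 define a failure as a CEC-confirmed AE, related to the system or procedure, that leads to one of the five listed outcomes by day 183.

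**Unknown relatedness, primary analysis.** SAP 7.9.1.2 treats an Unknown rating as not related: for an Unknown "classification relationship to the Micra TPS and/or procedure, the event will not be considered" related. The same section notes: "Only system or procedure-related AEs will be classified as a major complication, minor complication or an observation". An Unknown AE therefore receives none of those three labels under the definitions.

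**Unknown relatedness, sensitivity analysis.** The rule in SAP 7.9.1.4 opens "In the event the CEC adjudicates an AE with an" Unknown rating, adds that the subject has no other failure within 6 months, and concludes that "a sensitivity analysis will be conducted to consider those subjects as failures at the time of the first" Unknown event. Outcome, seriousness and severity are not mentioned.

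**Deaths of unknown cause.** Protocol 14.1.7 allows the worst-case analysis for truly missing data "or if the cause of death is unknown", and then says "The sensitivity analysis may count such missing data as failures". SAP 7.4 and 7.9.1.4 repeat the worst-case rule for truly missing data without the death clause, and the visible text gives no reason.

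**The concern.** A sensitivity analysis for unclear relatedness should ask what happens to the primary result if the doubtful events were in fact related. That means relaxing relatedness and keeping everything else. The SAP rule also removes the outcome requirement, so it estimates freedom from a mixture of related major complications and any AE of unknown relatedness. A brief, self-limiting AE would count the same as a cardiac perforation.

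This is the only mandatory rule in the visible SAP for unclear relatedness, in a single-arm trial whose endpoint depends on the CEC's relatedness judgement. If the analysis falls below 83%, nobody can tell from it whether the pass is fragile or whether a few trivial AEs were counted. If an outcome filter is then added after the data are seen, the analysis is no longer pre-specified.

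**Working it through.** **Inputs**
- Performance criterion 83%, expected rate 94%, two-sided 0.05, 80% power, 10% attrition, N = 82 (Protocol 14.1.2.2, SAP 6.2).
- Kaplan-Meier estimate with log-log limits; pass if the two-sided 95% lower limit exceeds 83% (SAP 7.9.1.2).
- Number of subjects whose only event is an Unknown AE: not given in the documents. I assume 0 to 3.

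**1. The plan's own figure.**
n = [1.960·√(0.83·0.17) + 0.842·√(0.94·0.06)]² / 0.11² = 72.4, rounded up to 73. Then 73/0.9 = 81.1, rounded up to 82. The stated size is reproduced.

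**2. How many failures the pass rule tolerates.** With no early censoring, the Greenwood variance is S(1−S)/n. The standard error of log(−log S) is se = √(S(1−S)/n) / (S·|ln S|), and the lower limit is S^exp(1.96·se).

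| n | failures | S | lower limit | against 83% |
|---|---|---|---|---|
| 82 | 5 | 93.90% | 85.97% | pass |
| 82 | 6 | 92.68% | 84.44% | pass |
| 82 | 7 | 91.46% | 82.93% | below |
| 74 | 5 | 93.24% | 84.53% | pass |
| 74 | 6 | 91.89% | 82.84% | below |

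(82 less 10% is 73.8, taken as 74.) The rule tolerates 6 failures of 82, or 5 of 74.

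**3. Illustration.** Five related major complications in 82 subjects pass at 86.0%. Add two subjects whose only event is a minor AE of unknown relatedness: 5 + 2 = 7 failures, lower limit 82.9%. The sensitivity analysis falls below 83% although no further event with a major-complication outcome has occurred.

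**4. Chance that the sensitivity analysis passes.** Let X be the number of true failures, binomial, and u the added Unknown subjects. The chance is P(X ≤ 6−u) at n=82, or P(X ≤ 5−u) at n=74.

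| n, true rate | u=0 | u=1 | u=2 | u=3 |
|---|---|---|---|---|
| 82, 94% | 77.9% | 63.0% | 45.0% | 26.8% |
| 82, 96% | 95.4% | 88.9% | 76.9% | 58.4% |
| 74, 94% | 71.6% | 54.1% | 34.5% | 17.2% |

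**5. Deaths, documents side by side.** Protocol 12.1.3 puts the AE leading to death on an AE form. SAP 7.10.2 has the CEC classify every death. A death whose AE is rated Unknown for relatedness is therefore already a failure in the mandatory analysis of SAP 7.9.1.4, whereas the Protocol's worst case is optional. What is left is a death of unknown cause that the CEC does not rate Unknown for relatedness. If it is rated not related, it is censored at the date of death (SAP 7.9.1.2), and no visible SAP analysis clearly covers it. Protocol 12.1.3 lists cause and relatedness as separate items, so the case is possible.

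**The case against.** **A narrower reading exists.** In SAP 7.9.1.2 the Unknown sentence follows directly on the CEC's decision about what is a major complication. In 7.9.1.4 the condition of no other failure suggests that the Unknown event would itself be a failure but for its relatedness. That may be what the authors meant, but 7.9.1.4 does not say it. SAP section 8 requires independent programming for analyses of the primary objective, and two programmers could reasonably produce different counts.

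**The error runs against the device, and pass/fail does not rest on it.** Both are true, and they limit the importance of the point. A conservative analysis is still of little use if it measures something else.

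**A reader might infer that the outcome filter cannot be applied**, because major, minor and observation labels are reserved for related AEs. The documents do not support that. The note restricts the labels, not the data: seriousness, actions and outcome are captured for reported AEs (Protocol 10.3), and deaths and system modifications are recorded separately (Protocol 12.1.3, 10.1.5). What is missing is the instruction, and a CEC confirmation of the outcome where relatedness is Unknown.

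**A reader might use Protocol Table 1 to size the effect**, since 54 − 28 = 26 of the complications there were not major. Those were related events, which this rule never touches, and they say nothing about how often the CEC will rate an AE Unknown.

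**A reader might infer that unexplained deaths generally escape scrutiny.** They do not, as step 5 shows. The Unknown death class (Protocol 12.1.3.1, SAP 7.10.4.3) also includes deaths without evidence for no relatedness, and the SAP's truly-missing rule gives its case only as an example, which leaves room for such deaths. The gap is narrow.

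**Conclusion.** The concern holds for the sensitivity rule. As written, SAP 7.9.1.4 drops the outcome requirement along with relatedness, so its result does not test the primary endpoint. The leverage per subject is large because only 6 failures of 82 (or 5 of 74) are tolerated: two added minor Unknown AEs cut the chance of passing this analysis from 77.9% to 45.0% at n=82 and a true rate of 94%. These figures assume no early censoring, independent subjects and an assumed number of Unknown AEs. They show sensitivity and are not a forecast.

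The primary analysis and its pass/fail decision are unaffected. The omitted death trigger is a real difference between Protocol and SAP, but a small one. It should not be read as a second failure of equal weight in the opposite direction.

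**What to change.** 1. In SAP 7.9.1.4, count a subject with an Unknown-relatedness AE as a failure only if that AE met one of the five major-complication outcomes on or before day 183. Date the failure at the onset of the first such AE.
2. Have the CEC confirm the outcome criterion for these AEs regardless of relatedness.
3. Report the result next to the primary result.
4. In SAP 7.4 and 7.9.1.4, either restore the Protocol's trigger for deaths of unknown cause, or state that the Unknown-relatedness rule replaces it. Restoring it does not require overriding the CEC: the Protocol only permits such deaths to be counted as failures, and Protocol 13.1 makes the CEC's classification the one used for analysis.

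The cost is some SAP wording and possibly a field on the CEC form, which is not among the documents. The sensitivity figure may move either way: the filter can remove failures, and the death trigger can add one. No extra subjects are needed, and the primary test does not change.

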7.9.2 Secondary Objectives

The secondary objectives will be analyzed using descriptive statistics.

7.9.2.1 Secondary Objective #1

Objective:

To demonstrate the effectiveness of Micra TPS

Cohort definition and analysis method:

All available pacing capture thresholds, pacing impedance and R-wave amplitude data from all successfully implanted subjects from the implant and scheduled follow-up visits will be included in this analysis.

Pacing capture thresholds, impedance and sensing amplitudes will be assessed and recorded at implant and each scheduled follow-up visit. Mean, standard deviation, and 2-sided 95% CI, as well as minimum, median and maximum values will be presented for each measurement at each visit.

Since Micra utilizes different battery technology, the system nominally paces at a shorter pulse duration (0.24ms vs. 0.4ms in traditional pacemakers). It is expected that most of the subjects will have pacing capture thresholds ≤ 2 volts at all visits.

All AEs collected during the study will be included in this analysis.

All information associated with each AE, including event description, severity, and relatedness to the system, etc., will be reported. In addition, the event rate will be summarized. The 2-sided 95% CIs will be calculated using the Exact Binomial method.

7.10.2 Deaths

Death information will be collected throughout the trial when the event occurs. Safety specialists will ensure that all deaths will be classified by the CEC. A summary table will be compiled with the death classification, as well as the relatedness to the procedure, system (including specific system component), accessory (including specific accessory or tool), and underlying condition or disease. The CEC classification of relatedness will be used. The number of events and percent of subjects will be provided.

7.10.3 Device Deficiency

In the event a device deficiency occurs, the data will be collected on the eCRFs. A listing will be compiled to summarize the device deficiency details, including description of the deficiency, date of onset, actions taken as a result of the deficiency, and the outcome of the event.

7.10.4 Adverse Event and Death Definitions

7.10.4.1 Relatedness

Procedure-related:

An event that is directly related to the implantation or modification procedure of a device/system.

System-related:

An AE that results from the presence or performance (intended or otherwise) of the device (e.g. Micra device, delivery catheter, or software).

Micra Implantable Device-related: An AE that results from the presence or performance (intended or otherwise) of the Micra device

Delivery Catheter-related: An AE that results from the presence or performance (intended or otherwise) of the delivery catheter

Software-related: An AE that results from the performance (intended or otherwise) of the Micra software

Accessory/Tool-related:

Programmer-related: An AE that results from the presence or performance (intended or otherwise) of the programmer

Introducer-related: An AE that results from the presence or performance of the introducer

Implant tool-related: An AE that results from the presence or performance of the implant tool (excluding delivery catheter and introducer)

Extraction tool-related: An AE that results from the presence or performance of the extraction tool

Note: If an event occurs because of a system component but it is unclear which component it is related to, the default will be to the last component used prior to the event being observed.

Hospitalization:

An overnight hospital admission, where admission date and discharge date are different

An unsuccessful implant is not considered an AE; however, any AEs occurring during an unsuccessful implant attempt (e.g. dissection, perforation) must be recorded and classified.

7.10.4.2 Complication

Complication:

An AE that results in death, involves any termination of significant device function or requires an invasive intervention.

Non-invasive when applied to a diagnostic device or procedure, means one that does not by design or intention:

- Penetrate or pierce the skin mucous membranes of the body, the ocular cavity or the urethra, or

- Penetrate: to pass, extend, pierce, or diffuse into or through something; to enter overcoming resistance; to gain entrance to
- Pierce: to force a way into or through something
- Enter the ear beyond the external auditory canal, the nose beyond the nares, the mouth beyond the pharynx, the anal canal beyond the rectum, or the vagina beyond the cervical os.

Blood sampling that involves simple venipuncture is considered noninvasive, and the use of surplus samples of body fluids or tissues that are left over from samples taken for non-investigational purposes is also considered noninvasive.

Major Complication:

A complication which results in:

- Death
- Permanent loss of device function due to mechanical or electrical dysfunction of the device (i.e. pacing function disabled, leaving device abandoned electrically)
- System revision (explant, reposition, replacement)
- Hospitalization
- Prolonged Hospitalization by 48 hours or more

Note: Only system or procedure related AEs will be classified as a major complication, minor complication or an observation

Minor complication:

Any AE classified as a complication that is not a major complication (e.g. event classified as a complication solely based on intravenous drug administration)

Observation:

Any AE that is not a complication.

7.10.4.3 Death Classification

Sufficient information will be required in order to properly classify the subject's death. The investigator shall classify each subject death per the following definitions:

Cardiac death:

A death directly related to the electrical or mechanical dysfunction of the heart.

Sudden cardiac death (SCD):

Natural death due to cardiac causes, indicated by abrupt loss of consciousness within one hour of the onset of acute symptoms; preexisting heart disease may have been known to be present, but the time and mode of death are unexpected. If time of onset cannot be determined, SCD will alternatively be defined as any unexpected cardiac death occurring out of the hospital or in the emergency room as dead on arrival.

Non-sudden cardiac death:

All cardiac deaths that are not classified as sudden deaths, including all cardiac deaths of hospitalized subjects on inotropic support.

Non-cardiac death:

A death not classified as a cardiac death.

Unknown:

A death in which there is no clinical evidence to support:

- A direct relatedness to the system component or
- A probable cause relatedness to the system component or
- No relatedness to the system component

7.11 Health Outcomes Analyses

Not applicable for this study.

7.12 Changes to Planned Analysis

This SAP has been developed prior to data being analyzed to further describe the statistical methods and planned analyses of the study data to be included in the clinical study report. Any change to the data analysis methods described in the CIP will require a CIP amendment only if it changes a principal feature of the CIP. Any other change to the data analysis methods described in the CIP or SAP, and the justification for making the change, will be described in the clinical study report.

8. Validation Requirements

All statistical analyses for the clinical study report will be carried out and validated by the Leading Institution authorized statistician(s). Levels of validation required for the different

elements of the clinical study report are specified in the table below. In addition, the full clinical study report will be independently validated by Medtronic personnel.

Table 6: Validation Requirement

Validation Level	Definition	Required for
Level I	A peer reviewer independently programs output and then compares the output with that generated by the original author of the program to be validated	All analyses in the CSR pertaining to the primary and secondary objectives of the study
Level II*	A peer reviewer reviews the program, and where appropriate, performs calculations or programming checks to verify the output	All other analyses in the CSR (not pertaining to the primary and secondary objectives of the study)

*Level II validation is the minimum requirement; alternatively, level I validation can be performed if desired since it is more rigorous.

9. References

1. Mallela VS, Ilankumaran V and Rao NS. Trends in cardiac pacemaker batteries. *Indian Pacing Electrophysiol J.* 2004;4:201-12.
